5.2 Treatment Administered

All patients in this study will be treated with the Prismaflex System Control Unit with Version 7.xx Software and the disposable Prismaflex M150 Set. The patients will be followed post-randomization for up to 120 hours from the initiation of study CRRT. This 120 hour post-randomization period will be referred to as the Treatment Period. At the time of randomization, if a patient is currently receiving CRRT, the standard-of-care CRRT extracorporeal circuit will be replaced with a new Prismaflex M150 Set. During the Treatment Period, patients will be treated up to 120 hours of study CRRT with either Prismocitrate 18 or no systemic anticoagulation. "Baseline" during the Treatment Period is defined as prior to any CRRT therapy, "Initiation" is defined as after randomization but before the initiation of study CRRT. Initiation may occur at the same time point as baseline, should enrollment and randomization occur prior to any CRRT therapy. Following data points will be collected during study CRRT for the duration of the Treatment Period:

- Extracorporeal circuit pressures will be measured and recorded by the Prismaflex System device in real time. The end of the extracorporeal circuit life will be defined by the occurrence of one or both of the following Prismaflex System alarms/conditions, if the alarms cannot be mitigated. At this point study CRRT will be terminated and the extracorporeal circuit replaced, because mitigation of the following alarms is not possible:
 - "Warning: Filter Clotted", and/or
 - "Advisory TMP Too High"

Note: The nurse at the clinical site will document the alarm and rationale to stop treatment on the eCRF. In addition, the Prismaflex logging information from the data cards (one card per patient) will be collected on an ongoing basis and anonymized data will be sent to Baxter for technical analysis. An Independent Adjudicator will make the final determination of the alarm cause (see Section 9.9 Primary Endpoint Adjudication).

- Serum bicarbonate and pH will be measured at baseline, initiation of study CRRT, at 6 hour intervals and at 120 hours or end of the Treatment Period (see Appendix 1).

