- For measurement of delivered dose, daily effluent volume (in mL) will be recorded from the Prismaflex System history screen. In the Prismaflex software, the starting time for the charting interval will be set (eg, at 8:00 am) and the volumes and doses will be stored for each day starting at that time. The effluent volume together with the patient's weight will be used to calculate delivered dose (mL/kg/hour). Note that *daily* weight will need to be obtained and recorded/entered each morning (eg, at 8:00 am) in the "System Tools" screen for determination of both prescribed and delivered dose as part of standard clinical practice for each patient receiving CRRT.
- For both study arms Systemic ionized blood calcium concentrations will be measured at baseline and initiation, 1 hour after initiation of CRRT (post-randomization) and then at 6 hour intervals up to 120 hours of CRRT (see Appendix 1).
 - For the Prismocitrate 18 Arm, the systemic ionized calcium must be measured 1 hour prior to the initiation of study CRRT. If initiation ionized calcium is less than 0.9 mmol/L, the investigator must correct the serum level to greater

than 0.9 mmol/L in order to begin CRRT. This corrected systemic ionized calcium will be considered the patient's initiation value (see Appendix 1).

- For Prismocitrate 18 Arm Only Post-filter blood iCa will be measured 1 hour after initiation of CRRT (post-randomization) and then at 6 hour intervals up to 120 hours of CRRT (see Appendix 1).
- Blood total calcium concentrations will be measured at baseline, initiation, 1 hour and every 6 hours during the 120 hour Treatment Period and at 120 hours or end of the Treatment Period from the initiation of study CRRT in each. In conjunction with simultaneous systemic iCa concentrations, the total calcium/iCa ratio (both measurements in mmol/L) will be determined (see Appendix 1).
- Serum electrolytes (sodium, potassium, chloride, phosphate, and magnesium, anion gap) and base excess will be measured at baseline, initiation and at 6 hour intervals of study CRRT (post-randomization) up to 120 hours (see Appendix 1).
- Blood urea nitrogen (BUN) and serum creatinine measurements will be measured at baseline, initiation and twice daily (post-randomization) up to 120 hours of study CRRT (see Appendix 1).

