8.5.2 Secondary Efficacy Endpoints

A descriptive summary of systemic and post-filter blood iCa concentrations as assessed baseline (systemic only), initiation (systemic only), 1 hour and every 6 hours from the initiation of study CRRT during the 120 hour Treatment Period and at 120 hours or end of the Treatment Period will be provided by treatment group. Post-filter blood iCa concentrations will only be presented for the Prismocitrate 18 Arm.

A mixed-effects model repeated measures (MMRM) analysis will be used to evaluate differences between treatment groups in the change from initiation of study CRRT in systemic iCa concentrations that are collected 1 hour and every 6 hours from the initiation of study CRRT during the 120 hours Treatment Period and at 120 hours or end of the Treatment Period. If justified, separate models will be carried out for patients who did and did not receive standard-of-care CRRT.

In addition, frequencies and percentages will be provided for systemic iCa < 1.1 mmol/L by time point and treatment group (threshold indicative of decrease in iCa despite adequate calcium compensation).

A descriptive summary of the daily delivered dose and overall delivered dose will be provided by treatment group. Differences between treatment groups in the percentage of overall prescribed dose actually administered will be assessed on a 5% significance level using a two-sided t-test or Wilcoxon rank sum test, as applicable. However, the statistical test will only be carried out conditional upon a significant test result for the primary endpoint at the time point of the interim analysis or final analysis. This hierarchical test procedure guarantees that the overall type 1 error is controlled and preserved at a maximum of 5%.

Secondary Efficacy Endpoints will be analyzed on the FA Set based on the randomized treatment groups (intent-to-treat principle).

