5.1.1 Baseline Definition

Baseline (BL) will be defined as the last measurement before the initiation of CRRT. If a patient has not been on standard-of-care CRRT, the Baseline and Initiation labs will be the same. In this case, the acceptable baseline laboratory measurements can be up to 1 hour after initiation of CRRT.

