13.3 Secondary Analysis

A descriptive summary of systemic and post-filter blood iCa²⁺ concentrations as assessed at baseline (systemic only), 1 hour and every 6 hours during the 120 hours evaluation period and at 120 hours or end of the Evaluation period will be provided by treatment group. This summary will use the number of subjects n, mean, standard deviation, minimum, median and maximum. Changes from baseline will be analyzed by the number of subjects n, mean and standard deviation and t-test or Wilcoxon rank sum test, as applicable.

The individual blood iCa²⁺ concentrations will further be displayed graphically over time for each of the two treatment groups.

A MMRM analysis will be deployed to evaluate differences between treatment groups in blood i Ca^{2+} concentrations that are collected at baseline, 1 hour and every 6 hours during the 120 hours Evaluation period and at 120 hours or end of the Evaluation period from the initiation of CRRT. The model will include the illness severity score APACHE II, baseline i Ca^{2+} concentration, treatment group and time point as fixed effects, and an interaction between time point and treatment group will be included in the model only if treatment effects differ statistically significantly over time (p < 0.01).

In addition, frequencies and percentages will be provided for $iCa^{2+} < 1.1 \text{ mmol/L}$ by time point and treatment group (threshold indicative of decrease in iCa^{2+} despite adequate calcium compensation).

Daily delivered dose and overall delivered dose (both in mL/kg/hour) will be summarized using the number of subjects n, mean, standard deviation, minimum, median and maximum, as applicable. Treatment exposure will be analyzed carrying out the same descriptive summary for the percentages of the prescribed dose actually administered to the patient.

Effluent rate is considered an appropriate surrogate for the CRRT dose. Therefore, prescribed and delivered CRRT dose will be derived as follows based on the University of Alabama at Birmingham Continuous Venovenous Hemodiafiltration Protocol¹² used in the study:

$$Q_E = Q_{PBP} + Q_D + Q_{FR} + Q_R$$

where Q_E is the effluent rate (mL/hour),

Q_{PBP} is the pre-blood pump infusion rate which is the Prismocitrate 18 flow rate (mL/hour),

Q_D is the dialysate flow rate (mL/hour),

Q_{FR} is the patient fluid removal rate (mL/hour), and

Q_R is the post-filter replacement fluid rate (mL/hour).

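### The reference for change in systemic iCa is replaced by a corrected value in the Prismocitrate arm only, so it is not comparable between arms

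*Protocol*

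**What the plan says.** Protocol section 5.2 places initiation after assignment: it "is defined as after randomization but before the initiation of study CRRT". A sub-item limited to one arm then states: "For the Prismocitrate 18 Arm, the systemic ionized calcium must be measured 1 hour prior to the initiation of study CRRT". It continues: "If initiation ionized calcium is less than 0.9 mmol/L, the investigator must correct the serum level to greater" than that same threshold before CRRT may begin, and "This corrected systemic ionized calcium will be considered the patient's initiation value". Section 5.2.2.1 refers Control to the general CRRT guidelines and local practice. Nothing there replaces a Control patient's initiation value.

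Protocol section 8.5.2 uses a repeated-measures model (MMRM) for "differences between treatment groups in the change from initiation of study CRRT in systemic iCa concentrations".

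The SAP uses a different term, baseline. Section 5.1.1 defines it as the last measurement before CRRT starts. For patients without prior standard-of-care CRRT it adds that "the acceptable baseline laboratory measurements can be up to 1 hour after initiation of CRRT". Section 13.3 tests changes from baseline by t-test or Wilcoxon test. It also specifies an MMRM of the concentrations: "The model will include the illness severity score APACHE II, baseline" iCa, treatment group and time point. SAP section 12 declares no departures from the protocol.

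The sampling schedules (Protocol Appendix 1, SAP Table 2) put the pre-start systemic iCa draw one hour before study CRRT, in a row not limited to one arm. Footnote a makes baseline and initiation labs the same for patients without prior CRRT and allows ±1 hour around initiation. Footnote b allows ±1 hour around the on-treatment calcium draws.

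**The concern.** A randomised comparison of change needs a reference that assignment has not touched. Here, in an open-label trial, two patients with the same low iCa after randomisation are handled differently. The Prismocitrate patient's low value is overwritten by a corrected one. The Control patient's low value stays, unless local practice happens to correct and re-draw it. The low tail of the reference distribution is thus removed by rule in one arm only. Even with identical iCa during treatment, Control then shows more rise.

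The SAP does not remove the problem. The last measurement before CRRT is, for a corrected Prismocitrate patient, the corrected one. Adjusting for it conditions on a value that assignment has changed, which shrinks the bias without eliminating it.

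At stake is the planned between-arm comparison of change in systemic iCa, part of a stated secondary efficacy objective and also listed among the safety parameters.

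A second problem is not arm-specific: the plan can accept a reference lab drawn after study CRRT has begun.

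**Working it through.** The documents state no mean, SD, effect size or power for systemic iCa, so there is no plan figure to reproduce. From the documents: 80 per arm, two-sided 5% level, threshold 0.9 mmol/L. Assumed: uncorrected initiation iCa normal; corrected value c = 0.95; on-treatment SD 0.10, correlated 0.4 with the uncorrected value; no true treatment effect; no carry-over of pre-start calcium into on-treatment iCa. A single on-treatment value stands in for the MMRM.

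**Step 1: shift of the Prismocitrate reference mean.** With z = (0.9 - mean)/SD,

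s = c·Φ(z) - [mean·Φ(z) - SD·φ(z)].

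Example, mean 1.00 and SD 0.15: z = -0.667, Φ = 0.2525, φ = 0.3194. So s = 0.95×0.2525 - (0.2525 - 0.15×0.3194) = 0.2399 - 0.2046 = 0.0353.

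**Step 2: bias.** Unadjusted change is biased by -s. With baseline adjustment the bias is about -b·s, where b = 0.4×0.10/SD is the slope of on-treatment on uncorrected initiation iCa.

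**Step 3: false positives**, from 2,000 simulated null trials per setting.

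| Mean / SD | Share < 0.9 | s | b·s | Unadjusted | Adjusted |
|---|---|---|---|---|---|
| 1.10 / 0.10 | 2.3% | 0.0020 | 0.0008 | 6.6% | 5.4% |
| 1.10 / 0.12 | 4.8% | 0.0048 | 0.0016 | 6.4% | 5.4% |
| 1.05 / 0.12 | 10.6% | 0.0114 | 0.0038 | 9.9% | 6.0% |
| 1.05 / 0.15 | 15.9% | 0.0204 | 0.0054 | 15.5% | 6.5% |
| 1.00 / 0.15 | 25.2% | 0.0353 | 0.0094 | 40.5% | 9.2% |

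In the last row the simulated adjusted bias was about -0.010. A further 4,000 runs per setting, for shares of 2%, 11%, 16% and 25%, gave 6%, 9%, 15% and 40% unadjusted and 5%, 6%, 7% and 11% adjusted.

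The low end is close to nominal. In the first row the standard error of the difference in change is √[2×(0.01 + 0.01 - 2×0.4×0.01)/80] = 0.0173. A bias of 0.0020 is only 0.12 standard errors, so most of the excess over 5% there is simulation error.

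Harsher assumptions enlarge the effect. With correction to 1.00, mean 1.00, SD 0.15 both before and on treatment, and correlation 0.3 to 0.5, rejection was 43% to 53% unadjusted and 10% to 22% adjusted. At the other end, mean 1.15 and SD 0.08 put 0.1% below 0.9, with a shift under 0.001.

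**Step 4: uncorrected value as reference in both arms.** Bias fell within 0.001 mmol/L of zero, and rejection was 4.3% to 5.8% in every setting of the harsher grid.

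**Step 5: post-start window.** Initiation ±1 h spans -1 to +1 h, and the 1 h total-calcium draw ±1 h spans 0 to 2 h. They overlap from 0 to 1 h, so one total-calcium sample could be both reference and first on-treatment value. Bicarbonate, pH and the other electrolytes are next drawn at 6 h (5 to 7 h), so no overlap arises, though their reference could still be on-treatment. Systemic iCa is scheduled one hour before the start; even with ±1 h that spans -2 to 0 h, which conflicts with the SAP allowance.

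**The case against.** The strongest reply has five parts.

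- **Planned model.** The SAP model adjusts for baseline iCa, so its error rate is nearer 5% to 9% than 41%. This stands. The larger figures apply to unadjusted change, which SAP section 13.3 also tests.
- **Frequency.** Uncorrected severe hypocalcaemia is excluded in both arms, without a numeric limit, so few patients may start below 0.9. At 2%, the unadjusted bias is 0.002 mmol/L against a target band of 0.9 to 1.3. This stands as a limit on size; 25% is an assumption.
- **Control may be corrected too.** Protocol section 5.2.3 asks for notification at iCa below 0.9 without limiting it to one arm, and the SAP's last-measurement rule would pick up a re-drawn Control value. That is possible, but not required before the start, so it does not restore symmetry.
- **Carry-over and estimand.** If a fraction k of the pre-start rise persists, the unadjusted difference becomes -(1 - k)·s. At k = 0.4 in the worst row that is -0.6×0.0353 = -0.021, with about 16% rejection (about 7% adjusted). The adjusted difference becomes about (k - b)·s, here (0.4 - 0.267)×0.0353 = +0.005, so stronger carry-over reverses its sign. Under an uncorrected reference, k·s = +0.014 would be credited to Prismocitrate. That is an effect of assignment, not of CRRT alone, and is a fair reason to keep the corrected-value analysis as a sensitivity analysis. It does not justify an assignment-dependent reference in the main analysis.
- **Timing window.** A reader might infer that one tube serves as both reference and first on-treatment value for systemic iCa, or that the post-start window itself separates the arms. The documents support neither: the schedule puts that draw before the start, and the window applies to both arms and stems partly from Protocol Appendix 1.

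**Conclusion.** The concern holds in a limited form. The reference for change in systemic iCa is set after randomisation and is replaced by rule in one arm only. The SAP carries that value into its change scores and covariate.

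Without carry-over the direction is known: Prismocitrate appears to rise less or fall more. The size is not, because it depends on how many patients start below 0.9. Under the main assumptions the baseline-adjusted bias is about -0.001 to -0.010 mmol/L with 5% to 9% false positives (up to about 11%). For unadjusted change it is -0.002 to -0.035 mmol/L with about 6% to 41%.

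It would be wrong to infer that the trial's main conclusions are at risk. The circuit-life endpoint does not use iCa. The hierarchical procedure covers only the percentage of dose delivered. The absolute iCa summaries and the counts below 1.1 mmol/L do not use the reference. The total calcium/iCa ratio, the plan's specific indicator of citrate accumulation, is summarised separately.

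The post-start window is a smaller, separate inconsistency affecting patients without prior CRRT in both arms.

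**What to change.** Leave the clinical correction rule as it is and change only the analysis definitions:

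- Define the reference systemic iCa in both arms as the first value drawn after randomisation, before any pre-start correction and before study CRRT.
- Record the corrected value as a separate data point, and keep the analysis based on it as a sensitivity analysis.
- Treat any draw after study CRRT start as on-treatment for change scores and covariates.
- Use one reference term throughout Protocol sections 5.2 and 8.5.2, Appendix 1 footnote a, SAP sections 5.1.1 and 13.3, and SAP Table 2 footnote a. Reconcile the ±1 hour initiation window with the scheduled pre-start iCa draw.
- Declare any remaining departure from the protocol in SAP section 12.

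The cost is a short wording change to both documents and one derivation rule. The uncorrected value must have been measured, since it triggers the correction, but the documents do not show that the eCRF keeps it once replaced; that needs checking. A few patients without a pre-start draw would lose a change score.

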5.2.1 Cross-Over Patients

During the course of this clinical trial the assigned arms (Prismocitrate Group or Control Group) must be maintained for the duration of the study CRRT treatment if at all possible. Based on the controlled design of this study, the cross-over of patients is not allowed.

5.2.2 Study Arm Protocols

Participating investigator sites will use the following general guidelines for CRRT:

- Modality must be CVVHDF
- Minimum prescribed CVVHDF dose (based on total effluent volume) - 25 mL/kg/hour.
- Minimum BFR 100 mL/minute.
- Experimental Arm Maximum BFR 200 mL/minute.
- Control Arm Maximum BFR 400 mL/minute. This maximum BFR allows centers to follow their local standard-of-care procedures related to higher BFR use in non-anticoagulated circuits
- Minimum post-filter replacement fluid rate of 200 mL/hour for de-aeration chamber
- Minimum pre-blood pump infusion of 1000 mL/hour (either citrate or replacement fluid depending on the study arm)

5.2.2.1 Initial Prescription Orders for Control Arm

For the control arm, investigators are advised to use the general guidelines listed in Section 5.2.2 in combination with the standard-of-care practices per their local institution.

5.2.2.2 Initial Prescription Orders for the Prismocitrate 18 Arm

This initial prescription only applies to patients randomized to the Prismocitrate 18 Arm.

- Blood Flow Rate (Q_B): 100 to 200 mL/minute.
- The anticoagulant/replacement solution to be used is Prismocitrate 18, which at final concentration will provide: 140 mmol/L sodium, 86 mmol/L chloride, 18 mmol/L citrate.
- Minimal Initial Flow rate (mL/hour) of Prismocitrate 18 (delivered from the Prismaflex System PBP scale by the PBP pump): 1000 mL/hour.
 - The flow rate can be titrated by 100 mL/hour increments to maintain post-filter blood iCa levels < 0.4 mmol/L.

Rinse and prime the Prismaflex M150 Set according to the IFU. No heparin containing solutions should be used for priming.

After the initial citrate protocol prescription, the general guidelines outlined in Section 5.2.2 should be followed.

5.2.2.2.1 Effluent Rate

Total effluent rate (Q_E) (mL/hour) = Pre-blood pump (PBP) infusion rate (Q_{PBP}) + Post-dilution replacement fluid rate (Q_R) + Dialysate rate (Q_D) + patient fluid removal rate (Q_{FR}) .

- QPBP corresponds to the infusion rate of Prismocitrate 18.
- As specified in the Prismaflex M150 Set IFU, post-filter replacement fluid should be prescribed according to institutional practice for proper functioning of the deaeration chamber. The use of a calcium-containing post-dilution solution is not recommended.
- To calculate the hourly effluent rate to be prescribed, assume the effluent rate is a surrogate for the daily CRRT dose and the minimum prescribed dose is 25 mL/kg/hour with a minimum target delivered dose of 20 mL/kg/hour per 24 hours dose of treatment for both groups.
- The required effluent rate (mL/hour) can then be calculated by multiplying the patient weight (in kg) at the time of CRRT initiation by the target prescribed dose.
- For example, a 90 kg patient would require a total effluent rate of 2,250 mL/hour (90 kg x 25 mL/kg per hour). While adjustments in the infusion rates of Prismocitrate 18, post-dilution replacement solution, and dialysate can be titrated to meet the desired metabolic and anticoagulation requirements for the patient, the total effluent rate should not appreciably change, with maintenance of a minimum prescribed dose of 25 mL/kg/hour.

5.2.2.2 Blood Flow Adjustments

Based on the anticoagulation and metabolic requirements of the patient, a change in BFR should prompt consideration of the need for concomitant changes in the citrate infusion, post-dilution replacement fluid, and dialysate rates (as described in Section 5.2.2.2.1).

5.2.2.2.3 Dialysate Fluid Orders

• Ensure the dialysate contains no calcium.

5.2.2.4 Calcium Fluid Orders

5.2.2.4.1 Calcium Gluconate Fluid Orders

Calcium gluconate, 38.75 mmol/L (1 amp: 4.65 mEq or 93 mg elemental calcium) in 500 mL of normal saline 0.9%; IV Infusion, 60 mL/hour. The actual calcium calculations applied will be based on current standard-of-care for patients receiving CRRT.

REQUIRED:

- Maintain systemic blood iCa levels between 0.9 and 1.3 mmol/L.
- Monitor blood iCa level 1 hour after initiation and then every 6 hours, and adjust as needed to maintain post-filter blood iCa < 0.4 mmol/L.
- Post-filter blood iCa levels can be measured from the post-filter blood sample port (blue in color) located on the return line of the Prismaflex M150 Set; this level can be used to guide the Prismocitrate infusion rate.
- Potassium, phosphorus, and magnesium should be replaced separately, as needed.

5.2.2.4.2 Calcium Chloride Fluid Orders

Calcium chloride 108.8 mEq in 1 L of normal saline 0.9% (note-total bag volume is 1080 mL); IV Infusion, 60 mL/hour. The actual calcium calculations applied will be based on current standard-of-care for patients receiving CRRT.

REQUIRED:

- Maintain systemic blood iCa levels between 0.9 and 1.3 mmol/L.
- Monitor blood iCa level from patient 1 hour after initiation and then every 6 hours, and adjust as needed to maintain post-filter blood iCa < 0.4 mmol/L.
- Post-filter blood iCa levels can be measured from the post-filter blood sample port (blue in color) located on the return line of the Prismaflex M150 Set; this level can be used to guide the Prismocitrate infusion rate.
- Potassium, phosphorus, and magnesium should be replaced separately, as needed.

^{**}Calcium infusion should stop if CRRT is stopped.

^{**}Calcium infusion should stop if CRRT is stopped.

